7.2.5.2. Time to EXACT-defined recovery from index exacerbation

Time to EXACT-defined recovery from index exacerbation is defined as time from the date of randomisation until date of the first EXACT-defined recovery day during the 12-Week Treatment Period, where EXACT-defined recovery is described in Section 7.2.5.1. Participants who did not experience EXACT-defined recovery during the 12-Week Treatment Period will be censored at the date of their last dose of study treatment.

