7.2.2.1. Statistical analyses

Time to next exacerbation will be analysed using a Bayesian Cox proportional hazards model with the “Efron” method for handling ties.

Kaplan-Meier (KM) estimates of the probability of exacerbation will also be presented.

Non-informative priors will be used for all modelling parameters. Wherever possible conjugate priors will be utilised.

The hazard ratio and corresponding 95% HPD credible intervals for each nemiralisib dose versus placebo will be presented. The probability that the true hazard ratio is less than 1, in addition to other values appropriately selected based on the data, will be presented.

Based on pharmacological predictions, the 500 mcg and 750 mcg doses are expected to result in similar levels of target inhibition and thus potentially translate to similar clinical benefit, therefore an estimate of hazard ratio for pooled data from 500 mcg plus 750 mcg nemiralisib doses versus placebo will also be presented.

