7.2.5.4. Statistical analyses

The proportion of participants achieving EXACT-defined recovery from the index exacerbation will be analysed using a Bayesian logistic regression model. Separate models will be fitted for each time-point.

Non-informative priors will be used for all modelling parameters. Wherever possible conjugate priors will be utilised.

The results of the analysis will be presented in terms of odds ratios together with its associated 95% HPD credible interval. The probability that the true odds ratio is greater than 1, in addition to other values appropriately selected based on the data, will be presented.

Time to EXACT-defined recovery from index exacerbation will be analysed using the same techniques as described in Section 7.2.2.1.

Severity of subsequent HCRU-defined exacerbation(s) defined by EXACT will be summarised for each treatment group and reported by study period. The severity of subsequent HCRU-defined exacerbation(s) occurring whilst a participant is on treatment will be reported as during the 12-Week Treatment Period and the severity of subsequent HCRU-defined exacerbation(s) occurring after the last dose of study treatment will be reported as during the 12-Week Follow-up Period.

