7.3.1.1. Statistical analysis

Change from Day 84 in Clinic Visit trough FEV₁ will be analysed using the same techniques as described for Change from baseline in CAT Total Score in Section [7.2.6.3](#).

A subgroup analysis of change from Day 84 in FEV₁ will be performed by including a treatment-by-severity-by-Day term in the Bayesian Repeated Measures model.

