13.3. Appendix 3: Study Phases and Treatment Emergent Adverse Events

13.3.1. Study Periods

13.3.1.1. 12-Week Treatment Period

The 12-Week Treatment Period is assigned from Study Day 1 to Study Day 84.

13.3.1.2. 12-Week Follow-Up Period

The 12-Week Follow-up Period is assigned from Study Day 85 to Study Day 168.

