13.3.2. Study Phases

Exacerbation events during the 12-Week Treatment Period will be classified according to their occurrence from randomisation until treatment discontinuation/study withdrawal days, as detailed below.

Study Phase	Occurring from randomisation until
On-Treatment during the 12-Week Treatment Period	Treatment Stop Day
On- or Off-Treatment during the 12-Week Treatment Period	Day 84 or Study Withdrawal Day if Treatment Stop Day is < Day 84

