2.61.	MITT	Example 8	Statistical Analysis of Time to Next Exacerbation Following Cessation of Study Treatment by Index Exacerbation Severity		SAC
EXAcerbations of Chronic Pulmonary Disease Tool - Patient Reported Outcome (EXACT)					
2.62.	MITT	Example 9	Statistical Analysis of Proportion of Participants Achieving the EXACT-definition of Recovery by Visit		EOT, SAC
2.63.	MITT	Example 9	Subgroup Analysis of Proportion of Participants Achieving the EXACT-definition of Recovery by Index Exacerbation Severity		EOT, SAC
2.64.	MITT	Example 8	Summary and Statistical Analysis of Time to EXACT-defined Recovery		SAC

Efficacy: Tables					
No.	Population	IDSL / Example Shell	Title	Programming Notes	Deliverable [Priority]
2.65.	MITT	Example 10	Summary of Severity of Subsequent HCRU-defined Exacerbation During 12-Week Treatment Period	Also split by moderate and severe	SAC
2.66.	MITT	Example 10	Summary of Severity of Subsequent HCRU-Defined Exacerbation During 12-Week Follow-up Period	Also split by moderate and severe	SAC
2.67.	MITT	Example 35	Summary of Missing On-treatment EXACT-PRO data		EOT, SAC
2.68.	MITT	Example 35	Summary of Missing Off-treatment EXACT-PRO data		SAC
COPD Assessment Test (CAT)					
2.69.	MITT	Example 3	Summary of Change from Baseline in CAT Total Score		EOT, SAC
2.70.	MITT	Example 3	Summary of Change from Baseline in CAT Total Score by Index Exacerbation Severity		SAC
2.71.	MITT	Example 9	Statistical Analysis of Proportion of Responders Using the CAT Total Score by Visit		EOT, SAC
2.72.	MITT	Example 9	Subgroup Analysis of Proportion of Responders Using the CAT Total Score by Visit by Index Exacerbation Severity		SAC
2.73.	MITT	Example 11	Statistical Analysis of Change from Baseline in CAT Total Score (Repeated Measures Model)		EOT, SAC
2.74.	MITT	Example 11	Subgroup Analysis of Change from Baseline in CAT Total Score (Repeated Measures Model) by Index Exacerbation Severity		SAC
2.75.	MITT	Example 3	Summary of Change from End of Treatment in CAT Total Score		SAC
2.76.	MITT	Example 3	Summary of Change from End of Treatment in CAT Total Score by Index Exacerbation Severity		SAC
2.77.	MITT	Example 11	Statistical Analysis of Change from End of Treatment in CAT Total Score (Repeated Measures Model)		SAC

Efficacy: Tables					
No.	Population	IDSL / Example Shell	Title	Programming Notes	Deliverable [Priority]

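### Time to EXACT recovery counts events to Day 84 but censors non-recoverers at last dose, and its borrowed posterior probability points away from benefit

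*SAP*

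**What the plan says.** The event in section 7.2.5.2 is "time from the date of randomisation until date of the first EXACT-defined recovery day during the 12-Week Treatment Period". Nothing restricts it to recoveries while on treatment. Section 13.3.1 defines the period by calendar: "The 12-Week Treatment Period is assigned from Study Day 1 to Study Day 84". Section 13.3.2 confirms that the period contains off-treatment time. Its on- or off-treatment phase runs to "Day 84 or Study Withdrawal Day if Treatment Stop Day is < Day 84".

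The censoring rule in section 7.2.5.2 is: "Participants who did not experience EXACT-defined recovery during the 12-Week Treatment Period will be censored at the date of their last dose".

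On method, section 7.2.5.4 says: "Time to EXACT-defined recovery from index exacerbation will be analysed using the same techniques as described in Section 7.2.2.1". The posterior probability named in section 7.2.2.1 is "The probability that the true hazard ratio is less than 1", together with other values to be chosen from the data. For the proportion recovered, section 7.2.5.4 itself reports the probability that the odds ratio exceeds 1.

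**The concern.** The event window and the censoring date belong to different estimands. Take a participant who stops treatment on Day 10. If recovery comes on Day 40, the record is an event on Day 40, with 30 further days at risk. If recovery never comes, the record is censored on Day 10. After the last dose the risk set keeps future recoverers and drops future non-recoverers. That is informative censoring built in by the derivation, whatever the true mechanism of stopping.

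At stake are the Kaplan-Meier recovery curve in every arm and, where tolerability differs by dose, the hazard ratio against placebo for a named secondary endpoint.

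The tail is a separate matter. Recovery is a favourable event, so a better drug has a hazard ratio above 1. The only probability named in section 7.2.2.1 suits exacerbations, where a lower hazard is better. Taken over unchanged, it would make the two recovery analyses point in opposite directions.

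**Working it through.** **1. Compare with the plan's own matched rules.** Section 7.2.2 defines two for exacerbations.

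| Rule | Events counted | Censoring of the rest |
|---|---|---|
| 7.2.2, on-treatment | while on study treatment | last dose |
| 7.2.2, on- or off-treatment | up to Day 84 | Day 84 or study withdrawal |
| 7.2.5.2, recovery | up to Day 84 | last dose |

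The recovery endpoint takes its events from the second rule and its censoring from the first.

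**2. Arithmetic illustration (assumed figures).** Take 100 participants with 70% true recovery by Day 84. Let 20 stop on Day 10, let nobody recover before then, and let stopping be unrelated to recovery. Later recoveries are 0.70 × 20 = 14 among stoppers and 0.70 × 80 = 56 among the others.

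- To Day 84, censored at Day 84: (14 + 56)/100 = 70%.
- On-treatment, censored at last dose: 20 leave on Day 10, and 56/80 = 70%.
- As written: only the 20 − 14 = 6 non-recovering stoppers leave on Day 10, and 70/94 = 74.5%.

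Both matched rules return the truth and the mixed rule does not.

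**3. Simulation.** The plan gives no recovery rate, stopping rate or event count for this endpoint, so there is no figure to reproduce and the rates below are assumptions. Recovery and discontinuation were exponential and independent, and all stoppers kept completing diaries.

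Kaplan-Meier recovery at Day 84 under the written rule (200,000 per arm):

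| True recovery | 10% stop | 20% stop | 30% stop |
|---|---|---|---|
| 50% | 51.6% | 53.2% | 55.2% |
| 70% | 71.2% | 72.6% | 74.5% |
| 85% | 85.9% | 86.8% | 87.8% |

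The overstatement runs from 0.9 to 5.2 points.

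Cox hazard ratio under the written rule with true HR 1 (40,000 per arm):

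| Stopping, placebo v active | 50% recover | 70% recover | 85% recover |
|---|---|---|---|
| 10% v 10% | 0.993 | 1.006 | 0.994 |
| 10% v 20% | 1.035 | 1.041 | 1.025 |
| 10% v 30% | 1.101 | 1.065 | 1.032 |
| 20% v 30% | 1.045 | 1.045 | 1.027 |

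In the same runs the two matched rules gave 0.99 to 1.01, which also shows the simulation noise.

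**4. Sensitivity, at 75% recovery.**

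- Stopping concentrated in the first two weeks (5% v 15–25%): 1.040 to 1.092.
- Only half of stoppers continue diaries: 1.016 to 1.033.
- Front-loaded recovery (Weibull shape 0.5), all continuing: 1.019 to 1.040.
- Half continuing and front-loaded recovery together: 1.013 to 1.021.

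**5. Tail.** With a normal posterior for log HR and an assumed standard error of 0.13, Pr(HR<1) = Φ(−ln HR/0.13).

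- HR 1.3: Φ(−2.02) = 0.022, so Pr(HR>1) = 0.978.
- HR 0.8: Φ(1.72) = 0.957, so Pr(HR>1) = 0.043.

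The probability named by cross-reference is high when the drug delays recovery.

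**The case against.** The strongest defence is that the sponsor meant on-treatment recovery. The plan uses the period name loosely elsewhere. Section 7.2.8 ends the treatment period at the day of last dose. Section 7.2.1 places off-treatment exacerbations in the follow-up period, timed from last dose. Section 7.2.5.4 does the same when reporting exacerbation severity. On that reading the censoring rule matches and there is no bias. What stands is that the intent is uncertain. The formal definition is still Days 1 to 84, section 7.2.1 also has an on- or off-treatment row within that period, and section 7.2.2 says so explicitly when it means on-treatment events. A programmer following section 7.2.5.2 literally would build the biased variable, and under either intent the sentence needs correcting.

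The list of displays includes a "Summary of Missing Off-treatment EXACT-PRO data" (Table 2.68). A reader might take this as proof that early stoppers keep their diaries to Day 84. It shows only that off-treatment diary data exist; for completers that is the diary after Day 84. Continuation among stoppers is an assumption, and the bias shrinks as it falls.

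A reader might also infer that a 95% probability of benefit would be printed as 5%. The plan does not support that. Table 2.64 uses Example Shell 8, which shows counts, hazard ratio and credible interval but no probability row. The two tails are complements, so no information is lost. The defect is an unstated direction.

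Nor does the same criticism carry to section 7.3.1.1, where FEV₁ change from Day 84 "will be analysed using the same techniques as described for Change from baseline in CAT Total Score". That endpoint measures what happens after treatment stops, and the probability of a negative difference is a sensible measure of lost effect.

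Finally, Example Shell 11 is a shared template. Its positive-difference label suits FEV₁ change from baseline and conflicts with section 7.2.6.3 only for CAT and, by reference, SGRQ.

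**Conclusion.** The mismatch in section 7.2.5.2 is real on the text and should be corrected. It overstates Kaplan-Meier recovery by roughly 1 to 5 points under the assumed rates. It moves the hazard ratio only if stopping differs between arms: to about 1.01 to 1.10 under a true value of 1, in favour of the arm with more stopping, and about 1.00 if stopping is equal. None of the rates comes from the plan.

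The bias is small. At a standard error of 0.13, a hazard ratio of 1.03 to 1.05 moves Pr(HR>1) from 0.50 to between Φ(0.23) = 0.59 and Φ(0.38) = 0.65. It would be too strong to conclude that the rule makes an ineffective dose look effective. Time to recovery is not in the futility rules or the endpoint lists for Interim Analyses 1 and 2, and the recovery proportion, with its MITT denominator, is unaffected.

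The tail point holds as an omission: section 7.2.5.4 should state the direction for time to recovery. The Shell 11 label is a minor alignment.

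**What to change.** In section 7.2.5.2, choose one pairing and state it:

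- count recoveries to Day 84 and censor non-recoverers at Day 84 or, if earlier, at study withdrawal or the last EXACT diary day; or
- count only recoveries while on treatment and censor everyone else at last dose.

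In section 7.2.5.4, state that Pr(HR>1) is reported for time to recovery, in line with Pr(OR>1) for the proportion recovered.

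As a minor alignment, label the CAT and SGRQ versions of Example Shell 11 as Pr Diff <0 to match section 7.2.6.3, and keep >0 for FEV₁ change from baseline. Leave section 7.3.1.1 as it is.

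The cost is a few sentences, one derived date and one shell label. No new data are needed.

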7.2.5.3. Severity of subsequent HCRU-defined exacerbation(s) defined by EXACT

Severity of subsequent HCRU-defined exacerbation(s) defined by EXACT is defined as the highest EXACT Total Score (not using the 3-day Rolling Average) during the period from date of onset of the subsequent HCRU-exacerbation until date of EXACT-defined recovery of subsequent exacerbation.

Note, in this case, the Maximum Observed Value and EXACT-defined recovery are derived using the date of onset of the subsequent HCRU-exacerbation.

Severity of subsequent HCRU-defined exacerbation(s) defined by EXACT will only be derived for participants who have had a subsequent exacerbation. If a participant has more than one subsequent exacerbation, severity will be calculated for each subsequent exacerbation.

7.2.5.4. Statistical analyses

The proportion of participants achieving EXACT-defined recovery from the index exacerbation will be analysed using a Bayesian logistic regression model. Separate models will be fitted for each time-point.

Non-informative priors will be used for all modelling parameters. Wherever possible conjugate priors will be utilised.

The results of the analysis will be presented in terms of odds ratios together with its associated 95% HPD credible interval. The probability that the true odds ratio is greater than 1, in addition to other values appropriately selected based on the data, will be presented.

Time to EXACT-defined recovery from index exacerbation will be analysed using the same techniques as described in Section 7.2.2.1.

Severity of subsequent HCRU-defined exacerbation(s) defined by EXACT will be summarised for each treatment group and reported by study period. The severity of subsequent HCRU-defined exacerbation(s) occurring whilst a participant is on treatment will be reported as during the 12-Week Treatment Period and the severity of subsequent HCRU-defined exacerbation(s) occurring after the last dose of study treatment will be reported as during the 12-Week Follow-up Period.

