2.2. Study Design

This is a Phase IIb, multicenter, randomized, stratified (by index COPD exacerbation severity [moderate or severe] and by whether or not the participant is in the PK Subgroup), double-blind (Sponsor Open), placebo-controlled, parallel-group study in participants who present with an acute moderate or severe exacerbation of COPD requiring Standard of Care (SoC).

This study consists of a Screening Period, a 12-Week Treatment Period and a 12-Week Post-Treatment Follow-Up Period. Randomization and the first dose of the double-blind study treatment administration (Visit 2/Day 1) should take place in the morning, as soon as possible following determination of eligibility and completion of the baseline measures, including the EXACT-PRO questionnaire for the day of randomization, and FEV₁ measurement and no later than 48 hours after the start of SoC.

PK Subgroup: Sparse PK sampling will be conducted in a subgroup of participants at selected sites. The PK Subgroup will be identical to the main study in terms of the study population, design, and conduct, with the exception of blood draws (3 per visit on Days 14 and 28) for PK analysis.

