5.2. Baseline Definitions

For all endpoints, the baseline value will be the latest pre-dose assessment with a non-missing value, including those from unscheduled visits. If time is not collected, Day 1 assessments are assumed to be taken prior to first dose and used as baseline.

Post-bronchodilator Baseline FEV₁ is defined as the latest FEV₁ measured prior to the first dose of study treatment and post-bronchodilator.

Pre-bronchodilator Baseline FEV₁ is defined as the latest FEV₁ measured prior to the first dose of study treatment and pre-bronchodilator.

Baseline CAT Total Score is defined as CAT Total Score measured prior to the first dose of study treatment on Day 1.

Baseline SGRQ Total Score is defined as SGRQ Total Score measured prior to the first dose of study treatment on Day 1.

Unless otherwise stated, if baseline data is missing no derivation will be performed and baseline will be set to missing.

A centred baseline will be derived for each participant by subtracting the mean baseline across all participants from each participant's baseline value. The 'centred' baseline may be used instead of Baseline in the statistical analyses to aid convergence.

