5.4. Examination of Covariates and Subgroups

5.4.1. Covariates

The list of covariates may be used in descriptive summaries and statistical analyses, some of which may also be used for subgroup analyses. The key covariates of interest are Index exacerbation severity, Smoking history and Region. Additional covariates of clinical interest may also be considered. The decision to include covariates in the model will be based on their impact on the model fit and/or convergence and will be detailed in the CSR.

A centred covariate will be derived for each participant by subtracting the mean covariate across all participants from each participant's covariate value. The 'centred' covariate may be used in place of the covariate in the statistical analyses to aid convergence.

Covariate	Details
Index exacerbation severity	Categorical variable (Moderate or Severe) derived using the stratification variable from the randomisation system.
Age (at screening)	Continuous variable derived as described in Section 13.6.2.1
BMI	Continuous variable derived using Height and Weight variables collected in eCRF: BMI = Weight (kg) / (Height (m)) ²
Gender	Categorical variable (Male or Female), collected in eCRF
Country	Categorical variable
Region	Categorical variable derived using Country as: 
 • Americas: Canada, Mexico, United States • Asia: Australia, Korea • Eastern Europe: Poland, Romania, Russia • Western Europe: France, Germany, Italy, Netherlands, Spain, Sweden, U.K.
Smoking history	Categorical variable (Current or Former), collected in eCRF
Baseline COPD maintenance therapy type	Categorical variable derived depending on data observed. Possible categories of interest are: Monotherapy vs. Dual therapy vs. Triple therapy
Index exacerbation type	Categorical variable: New or Relapse, derived using the question: "Other than the current prescription, for the index exacerbation, has the subject received oral/systemic corticosteroids and/or antibiotics for a COPD exacerbation within the last 7 days?" in the eCRF: New = No Relapse = Yes
Number of exacerbations in the previous 12 months	Categorical variable derived from "Total number of COPD exacerbations in the last 12 months" in the eCRF. Possible categories of interest are: 0 vs. 1 vs. ≥2
Baseline COPD ICS therapy use	Categorical variable (ICS Use or Non-ICS Use) derived from review of concomitant medications

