7.2.6.3. Statistical analyses

The proportion of responders using CAT will be analysed using the same techniques as described in Section 7.2.5.4.

Change from baseline/end of treatment in CAT Total Score will be compared between treatment groups using a Bayesian Repeated Measures analysis with covariates for baseline-by-Day interaction and treatment-by-Day interaction. Day will be fitted as a repeated effect within each participant.

All post-baseline scheduled visits will be included in the analysis using Day.

Non-informative priors will be used for all modelling parameters. Wherever possible conjugate priors will be utilised. An unstructured covariance matrix will be used to model the within-subject error.

Adjusted posterior median change from baseline and corresponding 95% HPD credible intervals will be summarised for each treatment by time-point, together with estimated treatment differences (GSK – Placebo) and corresponding 95% HPD credible intervals. The posterior probability that the true treatment difference is less than 0, in addition to other values appropriately selected based on the data, will also be presented.

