7.2.7.3. Statistical analyses

Change from baseline/end of treatment in SGRQ Total Score and the proportion of responders on the SGRQ Total Score will be analysed using the same techniques as described in Section [7.2.6.3](#).

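### The logistic models for CAT and SGRQ responders do not specify the participant's own baseline score, which costs some power but causes no bias

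*SAP*

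**What the plan says.** **Responder models.** SAP 7.2.5.4 states that the proportion with EXACT recovery "will be analysed using a Bayesian logistic regression model. Separate models will be fitted for each time-point". No covariate is named. Section 7.2.6.3 adds: "The proportion of responders using CAT will be analysed using the same techniques as described in Section 7.2.5.4". Section 7.2.7.3 says that "the proportion of responders on the SGRQ Total Score will be analysed using the same techniques as described in Section" 7.2.6.3, which leads back to 7.2.5.4.

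**Responder definitions.** A CAT responder has a fall of at least 2 points from baseline (7.2.6.1). An SGRQ responder has a fall of at least 4 points (7.2.7.1). Response is derived only for participants whose baseline is at least 2 (CAT) or 4 (SGRQ), and is counted cumulatively up to each day.

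**Baseline.** Section 5.2 reads: "Baseline CAT Total Score is defined as CAT Total Score measured prior to the first dose of study treatment on Day 1". It defines the SGRQ baseline in the same way.

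**Continuous models.** For change in CAT score, 7.2.6.3 specifies a "Bayesian Repeated Measures analysis with covariates for baseline-by-Day interaction and treatment-by-Day interaction". Section 7.2.7.3 applies that model to SGRQ.

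**General covariate rule.** Section 5.4.1 states: "The key covariates of interest are Index exacerbation severity, Smoking history and Region". It also says: "Additional covariates of clinical interest may also be considered". Inclusion depends on the effect on model fit and/or convergence and is to be reported in the CSR. The covariate table contains no baseline CAT, SGRQ or EXACT score.

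**The concern.** A responder on CAT or SGRQ is defined by change from the participant's own starting score, so that score predicts response. The plan recognises this at the extreme by deriving response only for participants whose baseline is high enough to permit the required fall. It also names baseline in the continuous analysis of the same questionnaires on the same days, but not in the dichotomised analysis.

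Two things are at stake. The first is efficiency: these secondary comparisons leave out a predictor that has already been collected. The second is pre-specification. Under 5.4.1 the baseline score could enter a responder model only by a choice made on the data. The design is sponsor-open (2.2) and Clinical Statistics sees unblinded interim data (3.1). The CAT and SGRQ responder models are already run at Interim Analysis 2 (13.11.6.2, Tables 2.29 and 2.32), when the arms are smallest.

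**Working it through.** The SAP states no power, sample size, responder rate, SD or correlation for these endpoints, so there is no planned figure to reproduce. The size was estimated by simulation under stated assumptions. Maximum-likelihood logistic regression stands in for a Bayesian fit with flat priors.

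**Why baseline predicts response.** Let baseline and follow-up have equal SD and correlation ρ. The correlation between the change and the baseline is then −√((1−ρ)/2):

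- ρ = 0.3: −0.59
- ρ = 0.5: −0.50
- ρ = 0.7: −0.39
- ρ = 0.9: −0.22

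The gain from adjustment should therefore be largest when ρ is low.

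**Setting A.** Baseline ~ N(0, 7²). Follow-up = ρ·baseline + √(1−ρ²)·7·e − 3 + δ·treatment, with e standard normal. A responder has a fall of at least 2. The criterion is z > 1.645, with 1500 trials per row. Cells show power without → with baseline.

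| ρ | 100 per arm, δ = −2.0 | 100 per arm, δ = −2.5 | 300 per arm, δ = −1.3 |
|---|---|---|---|
| 0.3 | 39.7% → 47.7% | 50.4% → 59.9% | 46.1% → 53.6% |
| 0.5 | 47.6% → 55.1% | 62.1% → 69.5% | 59.5% → 62.8% |
| 0.7 | 65.1% → 68.7% | 79.1% → 82.9% | 76.0% → 78.5% |

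The gains run from 2.5 to 9.5 points.

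**Where the gain comes from.** Setting A, 100 per arm, δ = −2, standard error of the log odds ratio (OR):

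- ρ = 0.3: 0.292 → 0.336 (ratio 1.15)
- ρ = 0.5: 0.294 → 0.324 (ratio 1.10)
- ρ = 0.7: 0.301 → 0.320 (ratio 1.06)

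The odds ratio moves from 1.51 to 1.69 at ρ = 0.3 and from 1.59 to 1.74 at ρ = 0.5. The z-value, ln(OR)/SE, therefore moves as follows:

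- ρ = 0.3: 0.412/0.292 = 1.41 → 0.525/0.336 = 1.56
- ρ = 0.5: 0.464/0.294 = 1.58 → 0.554/0.324 = 1.71

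The standard error rises, but the log odds ratio rises proportionately more, so z increases.

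**Setting B.** SD 8, placebo change −3, extra active change 2 points, two-sided 5%, 1000 trials per cell.

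| ρ | 100/100 | 300/100 | 300/300 |
|---|---|---|---|
| 0.3 | 23% → 29% | 31% → 37% | 53% → 63% |
| 0.5 | 28% → 32% | 38% → 43% | 67% → 76% |
| 0.7 | 43% → 47% | 58% → 63% | 87% → 89% |
| 0.9 | 84% → 86% | 94% → 95% | 100% → 100% |

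The squared z-ratio gives the equivalent gain in sample size. With 300/100 at ρ = 0.3 it is (1.64/1.45)² = 1.28. Across arm sizes the gain is about 26–28%, 17–21%, 9–13% and 2–4% at ρ = 0.3, 0.5, 0.7 and 0.9. The largest single power gain was 11 points (58.3% → 69.5%; 300/100, extra change 3 points, ρ = 0.3).

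**Cumulative response.** Both settings use one visit, whereas the plan counts response on or before each day. With three visits (assumed residual correlation 0.6, otherwise Setting A with δ = −2 and 100 per arm), the gains were about 7, 5 and 3 points at ρ = 0.3, 0.5 and 0.7.

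**Error rate with no effect.** The two-sided rate was 4.5–6.5% unadjusted and 4.4–4.9% adjusted in Setting B. The one-sided rate was 4.3–5.0% unadjusted in Setting A. Omission produces no systematic error.

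**The case against.** The strongest reply is that an unadjusted odds ratio is a legitimate choice and that 5.4.1 already leaves room for baseline. Both points have force. The SAP is silent rather than exclusionary: additional covariates are allowed, 5.2 contemplates baseline in statistical analyses generally, and a strong predictor would probably pass a model-fit criterion. A reader might infer that baseline is ruled out, but the text does not support that. What remains is that the one obvious covariate for these endpoints is left to a choice made on the data.

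It can also be said that the plan sets no success threshold for these endpoints, so power against a 5% criterion has no counterpart in it. The power figures are best read as a measure of information lost. The futility rules in 3.1.1.1 use FEV₁ and exacerbation rate, so no stopping rule depends on the responder models. The simulations have no floor at zero, and all their inputs are assumed. These points limit the size and importance of the concern but do not reverse its direction.

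Three stronger readings are tempting and fail:

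- **Omission widens the intervals.** In logistic regression the reverse holds: the adjusted standard error is 6–15% larger.
- **Chance imbalance biases the result.** It adds variance, which the unadjusted interval already reflects, and error rates stayed near nominal.
- **EXACT recovery and its time-to-event (Cox) model lose power in the same way.** The Day 1 diary is a baseline measure (2.2: "completion of the baseline measures, including the EXACT-PRO questionnaire for the day of randomization"). However, recovery is judged against the highest rolling average in the first 14 days after randomisation (7.2.5), not against Day 1. No gain has been shown there, and the CAT-type result does not transfer.

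**Conclusion.** The concern holds for CAT and SGRQ responders as a matter of efficiency and pre-specification, not validity. The responder models do not specify the participant's own baseline score, although it defines the outcome, is collected before dosing and is used in the continuous models of the same instruments. Adding it would raise the chance of detecting a true effect by roughly 2–10 points for correlations of 0.3–0.7. The gain is close to nothing at 0.9. These figures rest on assumed SDs of 7–8, a mean placebo change of −3, extra active changes of 1.3–3 points and arms of 100–300, none of which the SAP supplies. The simulated responder used the CAT threshold of 2 points; SGRQ was not simulated separately, so its gain is inferred from the same structure.

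**What to change.** In 7.2.6.3 and 7.2.7.3, state that each responder logistic model includes the centred Day 1 total score of the same instrument as a fixed covariate, at every time-point and every interim. State also that the reported odds ratio is conditional on baseline. Keep the raw responder counts and percentages of Example Shell 9 alongside it.

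The cost is SAP wording and one model term; no new data are needed. The real downside is that the conditional odds ratio is a different quantity from the unadjusted one, about 1.7 against 1.5 at correlation 0.3, so the two must not be interchanged and the intervals will be somewhat wider. A participant without a Day 1 score has no derivable change and would also drop out of the adjusted model. Because 7.2.6.1 and 7.2.7.1 divide by the whole MITT population, the plan should say how such participants are counted.

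For EXACT recovery, the Day 1 EXACT score may be considered as a prognostic covariate, but its benefit is not shown. The 14-day maximum should not be used as a covariate, because it is measured after randomisation.
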